9.3 Analysis Sets

For the purposes of analysis, the following analysis sets are defined:

Participant Analysis Set	Description
Screened population	All participants screened (i.e. who signed the ICF)
Safety population	All participants who received at least one dose of study intervention and have at least one postbaseline safety assessment;
ITT/mITT population	The ITT population will include all participants who received at least one dose of study intervention; The modified intention-to-treat (mITT) population will contain all treated participants having a Month 6 post-baseline assessment of the primary efficacy endpoint
PP population	The PP population will contain all participants in the mITT after exclusion of the participants who had major protocol deviations that could potentially affect the primary efficacy endpoint outcome for the participants
PK population	All participants who received at least one dose of study intervention and have at least one valid triptorelin concentration

ICF=informed consent form; ITT=intention-to-treat; mITT=modified ITT; PK=pharmacokinetics; PP=per protocol.

The primary efficacy analysis will be performed on the ITT population. Supportive analysis of the primary efficacy endpoint will be based on the modified intention-to-treat (mITT) and the PP populations.

The secondary efficacy analyses will be based on the ITT population. Supportive analysis of the secondary analyses may be performed on the PP population.

The analyses of safety data will be performed based on the Safety population.

The analyses of PK data will be performed based on the PK population.

9.4 Statistical Analyses

The statistical analysis plan (SAP) will be finalised before the first participant enters the study and it will include a more technical and detailed description of the statistical analyses described in this section. This section is a summary of the planned statistical analyses of the most important endpoints including primary and key secondary endpoints.

Other endpoints as well as demographic, baseline characteristics and disposition will be detailed in the SAP.

Statistical evaluation will be performed using Statistical Analysis System (SAS[®]) Version 9.4 (or higher if available).

9.4.1 General Considerations

9.4.1.1 Reasons for Exclusion from the Analyses

Any major protocol deviation will be described and listed and its impact on the inclusion of any participant in each analysis population will be specified. The final list of protocol deviations impacting each analysis population will be reviewed prior to database lock. The list may be updated, up to the point of database lock, to include any additional protocol deviations which may impact the analysis of each population.

9.4.1.2 Significance Testing and Estimations

For the primary efficacy endpoint, the summary statistics of number and percentage of participants and the exact two-sided 95% CI for a binomial proportion will be computed by SAS[®] using the exact binomial distributions on the ITT population (primary population of analysis), mITT and PP sets.

For secondary efficacy endpoints related to a change at Months 3, 6, 9 and 12 compared to baseline, the descriptive summary statistics (n, mean, SD, median, minimum, maximum) will be calculated on the ITT population. In addition, secondary efficacy endpoints may be performed on the PP set. Exact two-sided 95% CIs will also be constructed for all secondary endpoints expressed as percentages.

9.4.1.3 Statistical/Analytical Methods

Statistical analyses will be performed by an external Service Provider, managed by the Sponsor's Biometry department.

Demographic and Other Baseline Characteristics

Descriptive summary statistics (n, mean, SD, median, minimum, maximum) and frequency counts of demographic and baseline data (medical history, concomitant disease, predosing AEs and ongoing medical history, prior and concomitant medications and therapies) will be presented for the ITT, mITT and PP sets, as well as the Safety population.

Participant Disposition and Withdrawals

The numbers and percentages of participants screened and included in each of the analysis populations will be tabulated overall and by centre. The reasons for participant exclusions from each of the populations and primary reasons for study discontinuation will be tabulated.

Adjustment for Country/Centre Effect

Descriptive analysis will be carried out to evaluate any possible centre effect.

9.4.2 Analysis of Primary Endpoint

The primary endpoint in this study is the proportion of children with LH suppression defined as stimulated peak LH ≤ 5 IU/L after GnRH stimulation at Month 6. The number and percentage

of participants with LH suppression (stimulated peak LH ≤ 5 IU/L after GnRH stimulation) will be presented and its two-sided 95% CI using Clopper-Pearson method will be presented and calculated. A test to the null hypothesis ($P \leq 80\%$) will be performed with a (one-sided) type I error as 2.5%.

9.4.3 Analysis of Secondary Endpoints

- Proportion of children with LH suppression defined as stimulated peak LH ≤ 5 IU/L after GnRH stimulation at Months 3 and 12:

The number and percentage of participants with LH suppression (stimulated peak LH ≤ 5 IU/L after GnRH stimulation) will be presented at Months 3 and 12 and its two-sided 95% CI will be presented and calculated using the same method as primary efficacy endpoint.

- Change in basal serum LH and FSH levels at Months 3, 6, 9 and 12 compared to baseline:

A summary table for the basal serum LH and FSH levels will be provided with descriptive statistics (n, mean, SD, median, minimum and maximum) at Baseline, Months 3, 6, 9 and 12 and for absolute changes from Baseline.

- Change in peak serum LH and FSH level after the GnRH stimulation test at Months 3, 6 and 12 compared to baseline:

A summary table for the peak LH and FSH levels after the GnRH stimulation test will be provided with descriptive statistics (n, mean, SD, median, minimum and maximum) at Baseline, Months 3, 6 and 12 and for absolute changes from Baseline.

- Proportion of children with pre-pubertal levels of sex steroids (defined as oestradiol ≤ 20 pg/mL [<73 pmol/L] in girls or testosterone ≤ 30 ng/dL [<0.8 nmol/L] in boys) at Months 3, 6, 9 and 12:

The number and percentage of participants with pre-pubertal levels of sex steroids (defined as oestradiol ≤ 20 pg/mL in girls or testosterone ≤ 30 ng/dL in boys) will be presented at Months 3, 6, 9 and 12. The two-sided 95% CIs will be presented and calculated using the same method as primary efficacy endpoint.

- Change in height (Z-score [height for age] and percentile for height for age) and growth velocity at Months 6 and 12 compared to baseline:

A summary table for the change in height (Z-score [height for age] and percentile for height for age) and growth velocity will be provided with descriptive statistics (n, mean, SD, median, minimum and maximum) at Months 6 and 12. In addition to the study endpoint on the change in height (Z-score and percentile) at Months 6 and 12, a summary table for the height absolute Z-scores and percentiles will be provided with descriptive statistics (n, mean, SD, median, minimum and maximum) at Baseline, Month 3, 6, 9 and 12.

- Proportion of children in whom the BA (Greulich and Pyle method):CA ratio did not rise at Months 6 and 12 relative to baseline (X-ray):

The number and percentage of participants without increase of bone age (Greulich and Pyle method)/chronological age ratio from Baseline to Months 6 and 12 will be presented and its two-sided 95% CI will be presented and calculated using the same method as primary efficacy endpoint.

- Change in difference between BA and CA and ratio BA:CA at Months 6 and 12 compared to baseline:

A summary table for the difference between BA and CA and ratio BA:CA will be provided with descriptive statistics (n, mean, SD, median, minimum and maximum) at Baseline, Month 6 and Month 12 and for absolute changes from Baseline.

- Proportion of children who achieve stabilisation of sexual maturation compared to baseline stage using Tanner method at Months 6 and 12:

The number and percentage of participants with no increase in Tanner puberty staging from Baseline to Months 6 and 12 will be presented and its two-sided 95% CI will be presented and calculated using the same method as primary efficacy endpoint.

- Proportion of girls with regression of uterine length at Months 6 and 12 (transabdominal ultrasound):

The number and percentage of girls with regression of uterine length at Months 6 and 12 will be presented and its two-sided 95% CI will be presented and calculated using the same method as primary efficacy endpoint.

- Proportion of boys with absence of progression of testis volumes at Month 6 and 12 (clinical assessment with orchidometer):

The number and percentage of boys with absence of progression of testis volumes at Months 6 and 12 will be presented and its two-sided 95% CI will be presented and calculated using the same method as primary efficacy endpoint.

- Change in body weight and BMI at Month 6 and 12:

A summary table for the body weight and BMI will be provided with descriptive statistics (n, mean, SD, median, minimum and maximum) at Baseline and Months 6 and 12 and for absolute changes from Baseline.

9.4.3.1 *Pharmacokinetic Analyses*

Individual listings of triptorelin concentrations and descriptive summary statistics (n, mean, standard error of mean (SEM), SD, coefficient of variance (%CV), geomean, geomean SD, geomean %CV, median, min, max, 95% CI) will be presented by timepoint/visit following each administration. If required and warranted by the data, an attempt to build a model to characterize the PK in the population will be made. An analysis to look at the relationship between concentrations versus efficacy and/or safety may be performed if warranted by the data. This will be described in a separate analysis plan and the outcomes summarised in a standalone report.

9.4.4 *Safety Analyses*

Safety endpoints are indicated in Section 3.

All safety data will be included in the participant data listings. Analyses and summary tables will be based on the Safety population.

All AEs will be coded according to the Medical Dictionary for Regulatory Activities (MedDRA) version (version in use before database lock) and will be classified by MedDRA preferred term (PT) and system organ class (SOC).

The incidence of all reported TEAEs, TEAEs associated with early withdrawal and SAEs will be tabulated overall. In addition, summary tables will be presented by maximum intensity and drug relationship.

A TEAE is defined as any AE that occurs during the active phase of the study if:

- It was not present prior to receiving the dose of triptorelin, or

- It was present prior to receiving the dose of triptorelin but the grade increased or became serious during the active phase of the study, or
- It was present prior to receiving the dose of triptorelin, the grade/seriousness is the same, but the causality changed to “related” during the active phase of the study.

All TEAEs will be flagged in the AE listings.

Summary incidence tables will be provided, classified by SOC, PT and associated National Cancer Institute – Common Terminology Criteria for Adverse Events (NCI-CTCAE) worst grade. In the event of multiple occurrences of the same AEs being reported for the same participant, the maximum intensity (Grade 5 > Grade 4 > Grade 3 > Grade 2 > Grade 1 > missing > not applicable) will be chosen. All AEs will be collected up to the EOS visit (see Table 2 for SoA).

Concomitant medication will be coded by using World Health Organization Drug Dictionary (WHO-DD) version (version in use before database lock) and will be summarised with the number and percentage of participants receiving concomitant medication by drug class and preferred drug name.

Haematological and biochemical toxicities will be recorded and graded according to the NCI-CTCAE criteria, where available. The NCI-CTCAE Grades 3 and 4 haematology and biochemistry variables will be listed by participant and by visit.

Actual values and changes from baseline in clinic 1 laboratory tests, physical examinations and vital signs will be summarised using descriptive statistics at each visit. For laboratory data, abnormal values will be flagged in the data listings and a list of clinically significant abnormal values will be presented. Shift tables using the worst on-treatment grade will be presented for the number and percentage of participants with NCI-CTCAE grades.

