3 OBJECTIVES AND ENDPOINTS

Table 4 displays the objectives and corresponding endpoints. Other attributes are described in further sections: Population in Section 5, study intervention in Section 6, prohibited medications in Section 6.8, analysis sets are defined in Section 9.3 and endpoints are described in further detail in Section 9.4.

Table 4 Objectives and Endpoints

Objectives	Endpoints
Primary	

 To assess the efficacy of the triptorelin 6-month PR formulation in suppressing LH levels to prepubertal levels (defined as a peak LH ≤ 5 IU/L) after i.v. GnRH stimulation at Month 6 (Day 169) in Chinese children with CPP 	
 Proportion of children with LH suppression defined as stimulated peak LH ≤ 5 IU/L after GnRH stimulation at Month 6.
Secondary	

 To assess the efficacy in suppressed LH response to GnRH test at Months 3 and 12 	
 Proportion of children with LH response to GnRH test at Months 3 and 12

 To assess change of basal serum LH and FSH levels at Months 3, 6, 9 and 12 	
 Change in basal serum LH and FSH levels at Months 3, 6, 9 and 12 compared to baseline

 To assess change of peak serum LH and FSH levels after the GnRH stimulation test at Months 3, 6 and 12 	
 Change in peak serum LH and FSH level after the GnRH stimulation test at Months 3, 6 and 12 compared to baseline

 To assess sex hormone serum concentrations (oestradiol for girls and testosterone for boys) at Months 3, 6, 9 and 12 	
 Proportion of children with pre-pubertal levels of sex steroids (defined as oestradiol ≤ 20 pg/mL in girls or testosterone ≤ 30 ng/dL in boys) at Months 3, 6, 9 and 12

 To assess height (Z-score [height for age] and percentile for height for age) growth velocity and BA (Greulich and Pyle method) at Months 6 and 12 	
 Change in height (Z-score [height for age] and percentile for height for age) and growth velocity at Months 6 and 12 compared to baseline Proportion of children in whom the BA/CA ratio did not rise at Month 6 and 12 relative to baseline (X ray) Change in the ratio BA/CA at Months 6 and 12 compared to baseline

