10.2 Appendix 2: Clinical Laboratory Tests

- The tests detailed in Table 6 will be performed either locally or centrally: safety clinical laboratory assessments will be done locally and only central assessment for hormone primary/secondary endpoints will be used in the analysis.
- Bioanalysis of PK samples will be done at a bioanalytical Service Provider.
- The preparation and storage of all samples are described separately in the laboratory manual.
- Protocol-specific requirements for inclusion or exclusion of participants are detailed in Section 5 of the protocol.
- Additional tests may be performed at any time during the study as determined necessary by the investigator or required by local regulations.

Table 6 Protocol-Required Safety Laboratory Tests

Parameters	Screening	Day 1	Month 3 (Day 85)	Month 6 (Day 169)	Month 9 (Day 253)	Month 12 (Day 337) EOS/ Discontinuation
Haematology [a]						
Complete blood count	X		X	X	X	X
Clinical Chemistry [a]						
Creatinine	X		X	X	X	X
Nonfasting Glucose [b]	X		X	X	X	X
Aspartate Aminotransferase (AST)	X		X	X	X	X
Alanine Aminotransferase (ALT)	X		X	X	X	X
Alkaline Phosphatase	X		X	X	X	X
Total and direct bilirubin	X		X	X	X	X
Calcium	X		X	X	X	X
Phosphorous	X		X	X	X	X
Routine Urinalysis [a]						
Specific gravity	X		X	X	X	X
pH, glucose, protein, blood, ketones, bilirubin, urobilinogen, nitrite, leukocyte esterase by dipstick	X		X	X	X	X
Microscopic examination (if blood or protein is abnormal)	X		X	X	X	X
Pregnancy testing						
Urine human chorionic gonadotropin (hCG) pregnancy test (as needed for WOCBP)	X					X
Other Hormone Tests						
Basal serum LH and FSH	X		X	X	X	X
GnRH test with LH and FSH	X		X	X		X
Oestradiol or testosterone	X		X	X	X	X

EoS=end of study; FSH=follicle-stimulating hormone; LH=luteinising hormone; WOCBP=women of childbearing potential

Notes:

Clinical laboratory tests will be performed either locally or centrally: safety clinical laboratory assessments will be done locally. For hormone primary/secondary endpoints only central assessment will be used in the analysis.

- If the screening tests performed within 1 week prior to Day 1, clinical laboratory assessments (haematology, clinical chemistry and urinalysis) will not be repeated on Day 1.
- In case of abnormal blood glucose as per investigator's judgement, repetition of these tests will be performed before the injection and fasting status might be required.

Investigators must document their review of each laboratory safety report.

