5.1 General Considerations

The precision of the measurement for each continuous variable will be used to determine the number of decimal places to present in tables, figures, and derived listings. Unless otherwise specified, min and max values will be reported with the same decimal as the units of measure; the mean, median and standard deviation (SD), will be reported to 1 greater decimal place, all of them will not be greater than 4 decimal places. Any values that require transformation to standard units (metric or International System [SI]) will be converted with the appropriate corresponding precision.

Percentages of categorical variables will be presented to 1 decimal place unless otherwise specified.

For laboratory values data below the lower limit of quantification (LLOQ) like “<xxx” or “<=xxx”, or above the upper limit of quantification (ULOQ) like “>xxx” or “>=xxx”, LLOQ or ULOQ (xxx) will be used for calculation of descriptive statistics. The original laboratory values (“<xxx”, “<=xxx”, “>xxx” or “>=xxx”) are presented in the listings.

All statistical analyses will be performed using the SAS® software version 9.4 or above version.

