5.1.1 Outputs Presentation

5.1.1.1 Tables Header

Since this is a single-arm study, all summary tables will be presented by Female, Male and Overall.

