AEs will be counted as follows:

- Participants with more than one AE within a particular SOC are counted only once for that SOC. Similarly, participants with more than one AE within a particular PT are counted only once for that PT;

- Participants reporting a TEAE more than once within that SOC/ PT, the TEAE with the worst-case grade (grade order: 5>4>3>2>1>missing) will be used in the corresponding grade summaries;
- Participants reporting a TEAE more than once within that SOC/ PT, the TEAE with the worst-case relationship to study medication (order: related > not related > missing) will be used in the corresponding relationship summaries;
- If the CTCAE grade is missing for a TEAE, it will be considered as missing in the summary tables;
- Summary by CTCAE grade will be presented (in the same order as above);
- If the causality is missing for a TEAE, it will be considered related in the summary tables;
- The non-serious TEAEs table should include a specific row “any non-serious TEAE above 10%”;
- A TEAE is counted only in the study where it started (if there is a change in the CTCAE grade, an additional AE should have been collected in the eCRF).

In addition, a listing with all AEs data will be listed by gender group including non-TEAEs, Treatment-emergence status will be flagged in the listing. Listing of Drug-related AEs will also be added.

The following listing will also be provided:

- A listing of all deaths that occurred during the study,
- A listing of all serious adverse events,
- A listing of all adverse events leading to discontinuation of study treatment.

Local tolerability Abnormalities

The following summary tables will be provided:

- A summary of the number and percentage of participants reporting a local tolerability reaction, by gender, SOC and PT,

The following listing will be provided:

- A listing of all local tolerability reactions that occurred during the study.

5.8.4 *Laboratory Data*

All laboratory data will be presented in the units of International System of Units (SI).

Describe the summaries that are to be provided. These may include the following summaries:

- A summary of the actual and change from baseline in each laboratory parameter by gender group and timepoint,
- A shift from baseline to worst post-dose (i.e. highest grade) in CTCAE Grade of laboratory results.

For shift tables, the denominator should be the number of participants with both a baseline and a post-baseline assessment at a given timepoint.

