Percentages will be presented to one decimal place. Percentages will not be presented for zero counts. Percentage will be calculated using n as denominator. The denominator n will be specified in a footnote for clarification if necessary. If sample sizes are small, the data displays will show the percentages, but in the CSR only frequency counts should be described.

P-values will be reported to four decimal places (e.g.: p=0.0037), after rounding. P-values which are less than 0.0001 will be presented as '<0.0001'.

All values below or above a limit of detection (e.g. <0.1 or >100) will be listed as such.

Dates will be presented in the format [ddmmmyyyy] and times in the format [hh:mm].

A4. Listings Conventions

Any listings will contain at least the following data: participant identifier, age and gender. When dates are presented, the associated study days should be included. They should be sorted by gender group then participant identifier. For multicentre studies, listings should be broken down by centre and gender group.

Note: In this study (D-CN-52014-244), any listings will contain at least the following data: participant identifier, age and gender. All listings should be sorted by participant identifier.

A5. Z-score and Percentile for Height for Age

The external file (CDCref_d.xls) from Division of Nutrition, Physical Activity, and Obesity of American CDC contains the L, M, and S parameters needed to generate exact percentiles and z-scores along with the percentile values for the 3rd, 5th, 10th, 25th, 50th, 75th, 90th, 95th, and 97th percentiles by sex (1=male; 2=female) and single month of age. Age is listed as interval in the external file; for example, _AGEMOS1=8.5, _AGEMOS2=9.5 months represents 8.5-9.4999 months. To obtain L, M, and S values at finer age or length/stature intervals interpolation could be used.

The LMS parameters are the median (M), the generalized coefficient of variation (S), and the power in the Box-Cox transformation (L). To obtain the value (X) of a given physical measurement at a particular z-score or percentile, use the following equation:

$$X = M (1 + LSZ)^{**}(1/L), L \neq 0$$

Or

$$X = M \exp(SZ), L = 0$$

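### The two printed limits for prepubertal testosterone are not equivalent: 30 ng/dL is about 1.04 nmol/L, not 0.8 nmol/L

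*Protocol*

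**What the plan says.** Sex-steroid suppression is a secondary endpoint, assessed at Months 3, 6, 9 and 12. The bullet that introduces it in Protocol 9.4.3 gives each hormone limit in conventional units, followed by a bracketed SI value:

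- Girls: oestradiol at or below 20 "pg/mL [<73 pmol/L] in girls".
- Boys: testosterone at or below 30 "ng/dL [<0.8 nmol/L] in boys".

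The Variable column of SAP Table 1 (section 5.7.3.1) prints the same pairs.

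Elsewhere the conventional limit stands alone. Protocol Table 4 gives 30 "ng/dL in boys) at Months 3, 6, 9 and 12" with no SI value. The synopsis table, the analysis sentence under the same bullet of Protocol 9.4.3, and the Endpoint column of SAP Table 1 do likewise. The figure 0.8 nmol/L never appears without 30 ng/dL beside it.

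Neither document gives a conversion factor, a separate source for 0.8 nmol/L, or a statement of which unit is used to classify response.

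**The concern.** A bracketed SI value after a conventional one reads as a conversion. The oestradiol bracket is a conversion, and the testosterone bracket is not a correct one. The definition of response in boys therefore carries two different cut-offs, in the protocol and again in the SAP column from which the variable would be programmed.

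If 0.8 nmol/L were applied, boys in the gap between the limits would be counted as non-responders, contrary to the endpoint tables. Few boys are expected and "all summary tables will be presented by Female, Male and Overall", so a single changed classification would be visible in the Male column. The primary endpoint, its test and the sample size do not depend on this limit.

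**Working it through.** **Inputs from the documents**

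- Testosterone limits: ≤30 ng/dL and <0.8 nmol/L. Oestradiol limits: ≤20 pg/mL and <73 pmol/L (Protocol 9.4.3; SAP Table 1).
- About 66 enrolled, at least three of them boys, and 62 treated (Protocol 9.2).
- Pivotal study: 5 boys among 44 children (Protocol 2.2).
- Recorded limits of <17.936 and <11.981 for oestradiol and testosterone, printed without units (SAP section 7).

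**Assumption.** The documents give no molar masses. From the molecular formulas, testosterone is 288.43 g/mol (range used: 288 to 289) and oestradiol is 272.39 g/mol.

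**Step 1: check the method on the oestradiol pair.** pmol/L = pg/mL × 1000 / molar mass.

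- 20 × 1000 / 272.39 = 73.4 pmol/L, against the printed 73. The plan's figure is reproduced.
- In reverse, 73 × 0.27239 = 19.88 pg/mL, a gap of 0.12 pg/mL.

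**Step 2: the testosterone pair.** nmol/L = ng/dL × 10 / molar mass.

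- 30 × 10 / 288.43 = 1.040 nmol/L (1.042 at 288; 1.038 at 289). The printed 0.8 is not reproduced.
- In reverse, 0.8 × 288.43 / 10 = 23.07 ng/dL (23.04 to 23.12).
- 0.8 / 1.040 = 0.769, so the bracket is 23% too low as a conversion.
- If 0.8 were itself rounded, 0.75 to 0.85 nmol/L is 21.6 to 24.5 ng/dL, still short of 30.
- For 0.8 to be right, the molar mass would have to be 300 / 0.8 = 375 g/mol.

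**Step 3: who is affected.** Only boys between about 23.1 and 30 ng/dL, a band of 30 − 23.07 = 6.93 ng/dL. All other boys are classified the same under either limit.

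**Step 4: effect of one reclassified boy at one visit.**

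| Denominator | Shift in proportion |
|---|---|
| Overall, 66 | 1/66 = 1.5 points |
| Overall, 62 | 1/62 = 1.6 points |
| Male column, 3 boys | 1/3 = 33 points |
| Male column, 7 or 8 boys (66 × 5/44 = 7.5) | 1/7 = 14.3; 1/8 = 12.5 points |

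**Step 5: what SAP section 7 implies about units.** The SAP does not say which of 17.936 and 11.981 belongs to which hormone.

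- If either were a testosterone limit in nmol/L, it would be at least 11.981 / 1.04 = 11.5 times the correct equivalent of 30 ng/dL. A result below it could not be classified, so nmol/L is implausible.
- If it is in ng/dL, the two figures convert to 17.936 × 10 / 288.43 = 0.62 nmol/L and 11.981 × 10 / 288.43 = 0.42 nmol/L. Both lie below 0.8, so a boy below quantification is a responder under either printed limit.

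**The case against.** The strongest reply is that the criterion is already clear. The endpoint tables, the operative analysis sentence and the Endpoint column of SAP Table 1 all use 30 ng/dL alone, and 0.8 nmol/L is only a gloss. Section 7 of the SAP points away from nmol/L as the working unit. Conversion details may also sit in the laboratory manual or the table shells, which are separate documents. Most of this stands, and it makes misapplication unlikely. It does not make the printed figure right, and no sentence tells a reader which limit to use when the two disagree.

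The 33-point figure is fairly called a ceiling. It needs exactly three boys, a value inside the band, and programming on the SI limit. The SAP also tempers it: "If sample sizes are small, the data displays will show the percentages, but in the CSR only frequency counts should be described".

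A reader might infer more, namely that SAP 5.8.4, which calls for laboratory data in SI units, obliges the programmer to classify on 0.8 nmol/L. The documents do not support that. Section 5.8.4 belongs to the safety section and governs how data are presented, not how responders are derived. Testosterone is an efficacy variable, and Protocol 10.2 separates locally run safety tests from centrally assessed hormone endpoints, even though Table 6 lists both. The general rule in SAP 5.1 ("Any values that require transformation to standard units (metric or International System [SI]) will be converted with the appropriate corresponding precision") is conditional and does not say that sex steroids need conversion.

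**Conclusion.** The concern holds as an error in the text with small consequences. The testosterone bracket in Protocol 9.4.3 and SAP Table 1 is not the equivalent of 30 ng/dL: it is 23% too low and corresponds to about 23.1 ng/dL. The result rests on an assumed molar mass, but no value near the true one closes the gap, and the same method reproduces the oestradiol bracket.

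The effect is confined to boys from about 23.1 to 30 ng/dL on one descriptive secondary endpoint. It is about 1.5 points overall per reclassified boy, and 33 points in the Male column if only three boys enrol. The documents do not show how likely a value in that band is. Use of 0.8 nmol/L is possible but unlikely. That view rests partly on an inference from limits printed without units.

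The strict sign inside both brackets, against at-or-below outside them, is a trivial difference.

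**What to change.** 1. The sponsor reconciles the two testosterone limits and confirms that the criterion in the endpoint tables (≤30 ng/dL) governs.
2. In Protocol 9.4.3 and the Variable column of SAP Table 1, delete the testosterone bracket or correct it to ≤1.04 nmol/L (1.04 × 28.843 = 30.0 ng/dL). Align the inequality signs in both brackets in the same edit.
3. Add one SAP sentence naming the unit in which sex-steroid response is classified, and state in SAP section 7 which hormone and unit each of 17.936 and 11.981 refers to.

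The cost is a bracket edit in two places and a short SAP clarification. Design, sample size and data collection are unaffected.
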